#### Abnormal Laboratory Findings and Other Abnormal Investigational Findings

Abnormal laboratory findings and other abnormal investigational findings (for example, on an ECG trace) should not be reported as AEs unless they are associated with clinical signs and symptoms, lead to treatment discontinuation, or are considered otherwise medically important by the Investigator. If a laboratory abnormality fulfills these criteria, the identified medical condition (for example, anemia, increased ALT) must be reported as the AE rather than the abnormal value itself.

#### **Adverse Drug Reaction**

An adverse drug reaction (ADR) is defined as any AE suspected to be related to M3541 or RT.

#### Serious Adverse Events

An SAE is any untoward medical occurrence that at any dose:

- Results in death
- Is life-threatening (Note: The term "life-threatening" refers to an event in which the subject is at risk of death at the time of the event, not an event that hypothetically might have caused death if it was more severe)
- Requires inpatient hospitalization or prolongs an existing hospitalization
- Results in persistent or significant disability or incapacity
- Is a congenital anomaly or birth defect
- Is otherwise considered to be medically important (Note: Important medical events that may not result in death, be life-threatening, or require hospitalization may be considered as SAEs when, based upon appropriate medical judgment, they may jeopardize the subject or may require medical or surgical intervention to prevent one of the outcomes listed above. Examples of such events include allergic bronchospasm requiring intensive treatment in an emergency room or at home, blood dyscrasias or convulsions that do not result in inpatient hospitalization, or the development of drug dependency or drug abuse).

For the purposes of reporting, any suspected transmission of an infectious agent via an IMP is also considered an SAE, as described in Section 7.4.1.4.

#### Events that Do Not Meet the Definition of an SAE

Elective hospitalizations to administer, or to simplify study treatment or study procedures (eg, an overnight stay to facilitate chemotherapy and related hydration therapy application) are not considered SAEs; however, all events leading to unplanned hospitalizations or unplanned prolongation of an elective hospitalization (eg, undesirable effects of any administered treatment) must be documented and reported as SAEs.

Document No. CC

Medical actions taken to reduce risks (like surgical interventions to prevent bone fractures of metastatic bone lesions) are not considered SAE despite requiring hospitalization of the subject.

#### Events Not to Be Considered as AEs / SAEs

Medical conditions present at the initial study visit (such as pain) that do not worsen in severity or frequency during the study (as compared with the subject's history) are defined as Baseline Medical Conditions, reported as medical history, and are not to be considered AEs.

#### AE / SAEs Observed in Association with Disease Progression

Progression of the disease / disorder being studied assessed by measurement of lesions on radiographs or other methods as well as associated clinical signs or symptoms (including laboratory abnormalities) should not be reported as an AE / SAE, unless the subject's general condition is more severe than expected for the subject's condition and / or unless the outcome is fatal within the AE reporting period (as defined in Section 7.4.1.3).

#### **Adverse Events of Special Interest**

To date, no AEs of special interest have been defined for M3541.

Specific toxicities identified during the conduct of the study will be closely monitored and specific instructions for monitoring and management of expected toxicities will be incorporated into the protocol and the IB. When further safety data for this drug combination become available, risk assessment and mitigation activities will be reviewed to assess the continued appropriateness.

#### 7.4.1.2 Methods of Recording and Assessing Adverse Events

At each study visit, the subject will be queried on changes in his or her condition. During the reporting period, any unfavorable changes in the subject's condition will be recorded as AEs, whether reported by the subject or observed by the Investigator.

Complete, accurate, and consistent data on all AEs experienced for the duration of the reporting period (defined below) will be reported on an ongoing basis in the appropriate section of the eCRF. All SAEs must be additionally documented and reported using the appropriate SAE eCRF page (SAESIDT) as described in Section 7.4.1.4.

It is important that each AE report include a description of the event, its duration (onset and resolution dates [and times when it is important to assess the time of AE onset relative to the recorded treatment administration time]), its severity, its causal relationship with the study treatment, any other potential causal factors, any treatment given or other action taken, including dose modification or discontinuation of the IMP, and its outcome. In addition, serious cases should be identified and the appropriate seriousness criteria documented. If an AE constitutes a DLT, this has to be documented accordingly.

Specific guidance can be found in the eCRF Completion and Monitoring Conventions.

## 7.4.1.3 Definition of the Adverse Event Reporting Period

The AE reporting period for safety surveillance begins when the subject is included into the study (date and time of first signature of informed consent) and continues through the study's 30-Day Short-term Follow-up visit, defined as 30 days after last M3541 / RT administration. After the 30-Day Short-term Follow-up visit only AEs that are deemed attributable to M3541 and / or RT by the Investigator should be documented until the End-of-Study visit, which is scheduled 1 year after the end of RT. Thereafter, the Investigator should contact the subject every 3 months ( $\pm$  1 month) until the defined end of the study (see Section 5.7) to enquire and monitor for late appearing RT-related toxicity.

Any SAE assessed as related to M3541 must be recorded and reported whenever it occurs, irrespective of the time elapsed since the last administration of M3541.

## 7.4.1.4 Procedure for Reporting Serious Adverse Events, Adverse Events of Special Interest and Dose-Limiting Toxicities

#### Serious Adverse Events

In the event of any new SAE occurring during the reporting period, the Investigator must immediately (within a maximum 24 hours after becoming aware of the event) inform the Sponsor or its designee using the SAE Report Form in the eCRF following specific completion instructions.

In exceptional circumstances, a SAE (or follow-up information) may be reported by telephone; in these cases, an SAE report form must be completed immediately thereafter in the eCRF.

Relevant pages from the eCRF may be provided in parallel (for example, medical history, concomitant drugs). Additional documents may be provided by the Investigator, if available (for example, laboratory results, hospital report, and autopsy report).

The Investigator must respond to any request for follow-up information (for example, additional information, outcome, final evaluation, or other records where needed) or to any question the Sponsor or designee may have on the AE within the same timelines as those noted above for initial reports. This is necessary to ensure prompt assessment of the event by the Sponsor or designee and (as applicable) to allow the Sponsor to meet strict regulatory timelines associated with expedited safety reporting obligations.

Requests for follow-up will usually be made via the responsible Monitor, although in exceptional circumstances the Global Drug Safety Department may contact the Investigator directly to obtain further information or to discuss the event.

#### **Dose-Limiting Toxicities**

Each event meeting the criteria of a DLT (see Section 5.1) must be recorded in the eCRF within 24 hours after becoming aware of the event. Any DLT meeting criteria for a SAE must also be reported in an expedited manner as SAEs as outlined above. Information on DLTs will be sent by

the Sponsor or delegate to the SMC core members within 1 working day of the receipt of documented information (ie, SAEs and / or DLTs).

#### 7.4.1.5 Safety Reporting to Health Authorities, Independent Ethics Committees / Institutional Review Boards and Investigators

The Sponsor will send appropriate safety notifications to Health Authorities in accordance with applicable laws and regulations.

The Investigator must comply with any applicable site-specific requirements related to the reporting of SAEs (particularly deaths) involving study subjects to the IEC / IRB that approved the study.

In accordance with ICH GCP guidelines, the Sponsor or designee will inform the Investigator of "findings that could adversely affect the safety of subjects, impact the conduct of the trial, or alter the IEC's / IRB's approval / favorable opinion to continue the trial." In particular and in line with respective regulations, the Sponsor / designee will inform the Investigator of AEs that are both serious and unexpected and are considered to be related to the administered product (suspected unexpected serious adverse reactions [SUSARs]). The Investigator should place copies of Safety Reports in the Investigator Site File. National regulations with regard to Safety Report notifications to Investigators will be taken into account.

When specifically required by regulations and guidelines, the Sponsor or designee will provide appropriate Safety Reports directly to the concerned lead IEC / IRB and will maintain records of these notifications. When direct reporting is not clearly defined by national or site-specific regulations, the Investigator will be responsible for promptly notifying the concerned IEC / IRB of any Safety Reports provided by the Sponsor or designee and of filing copies of all related correspondence in the Investigator Site File.

## 7.4.1.6 Monitoring of Subjects with Adverse Events

Adverse events are recorded and assessed continuously throughout the study (see Section 7.4.1.3) and are assessed for outcome at the PTD 30 Short-term Safety Follow-up Safety visit. All SAEs ongoing at the PTD 30 Short-term Safety Follow-up Safety visit must be monitored and followed up by the Investigator until stabilization or until the outcome is known, unless the subject is documented as "lost to follow-up" or the subject withdraws consent. Reasonable attempts to obtain this information must be made and documented. It is also the responsibility of the Investigator to ensure that any necessary additional therapeutic measures and follow-up procedures are performed.

A subject will be considered "lost to follow-up" if he or she repeatedly fails to return for scheduled visits and is unable to be contacted by the study site. The following actions must be taken if a subject fails to return to the clinic for a required study visit:

- The site must attempt to contact the subject and reschedule the missed visit as soon as possible, counsel the subject on the importance of maintaining the assigned visit schedule, and ascertain if the subject wants to or should continue in the study
- Before a subject is deemed "lost to follow-up", the Investigator or designee must make every effort to regain contact with the subject: 1) where possible, make 3 telephone calls; 2) if necessary, send a certified letter (or an equivalent local method) to the subject's last known mailing address, and 3) if a subject has given the appropriate consent, contact the subject's general practitioner for information. These contact attempts should be documented in the subject's medical record.
- Should the subject continue to be unreachable, he/she will be considered to have withdrawn from the study.

#### 7.4.2 Pregnancy and In Utero Drug Exposure

Only pregnancies considered by the Investigator to be related to study treatment (eg, resulting from a drug interaction with a contraceptive medication) are considered to be AEs; however, all pregnancies with an estimated conception date during the period defined in Section 7.4.1.3 must be recorded by convention in the AE page / section of the eCRF. The same rule applies to pregnancies in female subjects and to pregnancies in female partners of male subjects. The Investigator must notify the Sponsor or designee in an expedited manner of any pregnancy using the paper Pregnancy Report Form, which must be transmitted according to the same timelines as described for SAE reporting in Section 7.4.1.4.

Investigators must actively follow-up, document and report on the outcome of all these pregnancies, even if the subjects are withdrawn from the study.

The Investigator must notify the Sponsor or designee of these outcomes using the Pregnancy Report Form. If an abnormal outcome occurs, the SAE Report Form will be used if the subject sustains an event, and the Parent-Child / Fetus Adverse Event Report Form will be used if the child / fetus sustains an event.

Any abnormal outcome (eg, spontaneous abortion, fetal death, stillbirth, congenital anomalies, ectopic pregnancy) must be reported in an expedited manner as described in Section 7.4.1.4, while normal outcomes must be reported within 45 days after delivery.

In the event of a pregnancy in a subject occurring during the course of the study, the subject must be discontinued from study medication immediately. The Sponsor or designee must be notified without delay and the subject must be followed as mentioned above.

## 7.4.3 Clinical Laboratory Assessments

It is essential that the Sponsor be provided with a list of laboratory normal ranges before shipment of IMP. Any change in laboratory normal ranges during the study will additionally be forwarded to the CRO and the Sponsor.

All routine laboratory analyses will be performed at a laboratory facility local to the investigational site and relevant results must be drawn and checked before administration of M3541. The report of the results must be retained as a part of the subject's medical record or source documents. Blood samples for the tests listed below will be collected from subjects during the Screening phase as specified in the Schedules of Assessments (Table 1, Table 2, or Table 3 as appropriate).

Laboratory samples:

- Hemoglobin, reticulocytes, red blood cell count, complete white blood cell count (CBC), differential, and platelet count
- Serum chemistry profile, including AST, ALT, gamma-glutamyltransferase, total bilirubin (direct bilirubin when indicated), alkaline phosphatase, lactate dehydrogenase, creatine phosphokinase, amylase, lipase, sodium, potassium, calcium, phosphorus, magnesium, chloride, glucose, total protein, albumin, blood urea nitrogen/urea, uric acid, creatinine, and creatinine clearance
- Coagulation parameters international normalized ratio and activated partial thromboplastin time
- Urinalysis: dipstick followed by microscopic examination if abnormal results
- Serum pregnancy test at Screening. If confirmation of a subject's postmenopausal status is necessary, a FSH level will also be performed at Screening, see Section 7.1.1
- Pregnancy testing will be conducted at the end of relevant systemic exposure of the study intervention, ie, at PTD 15 (see Table 1).
- Hepatitis screening: If hepatitis B surface antigen positive and hepatitis B core antibody positive, then reflex to quantitative HBV DNA (PCR); if hepatitis B core antibody positive alone, then reflex to quantitative hepatitis B DNA (PCR); if hepatitis C antibody positive, then reflex to quantitative hepatitis C RNA (PCR).

#### 7.4.4 Vital Signs, Physical Examinations, and Other Assessments

Vital signs, including body temperature, respiratory rate, pulse (after 5-minute rest), arterial blood pressure (after 5-minute rest), and body weight and height (height only at Screening), physical examination, and ECOG PS will be recorded at Screening and at subsequent visits as indicated in the Schedules of Assessments (Table 1, Table 2, or Table 3 as appropriate) and documented in the eCRF.

The 12-lead resting ECGs will be obtained after the subject has been in a semi-supine position for at least 5 minutes predose and postdose and prior to any associated clinical laboratory (ECG should be obtained using a Holter recorder), PK or pharmacodynamics sample blood draws. All ECGs will be evaluated by the Investigator for safety assessment. At specified time points during the treatment period (Table 4, Table 5, or Table 6 as appropriate), additional digital ECG recordings, equivalent to triplicate ECGs, are to be recorded at the indicated times for quantitative analysis by a central ECG laboratory (at the end of the study).

The time windows for postdose ECGs are  $\pm 5$  minutes for ECGs up to 1 hour after administration of M3541,  $\pm 15$  minutes for postdose ECGs up to and including 4 hours, and  $\pm 30$  minutes for all

CCI

others. Electrocardiograms to be sent for evaluation, must be time-linked to the PK samples scheduled for the respective time points, with the PK blood sample withdrawn immediately after the ECG recording.

All newly diagnosed or worsening conditions, signs and symptoms observed after the signing of the ICF, whether related to study treatment or not, are to be reported as AEs and documented in the eCRF Adverse Event section (see Section 7.4.1). Abnormal findings are to be reassessed at subsequent visits.

For female subjects of childbearing potential (see Section 7.1.1) serum  $\beta$ -HCG pregnancy test will be carried out during the Screening and urine  $\beta$ -HCG test will be performed according to the Schedules of Assessments (Table 1, Table 2, or Table 3 as appropriate).

## 7.4.5 Tumor Pain

All subjects will be asked to complete the BPI-SF at Screening and FD 1 prior to other study-related assessments. If a subject has no pain in an area to be irradiated as part of the experimental treatment (M3541 + RT), the subject should mark "0" in all pain scales and activity scales. For subjects with cancer pain from lesions to be irradiated as part of the experimental treatment, any pain medication should be documented (name, dose, frequency, including if used on an "as needed" basis) on the appropriate eCRF page.

Subjects with cancer pain from lesions to be irradiated as part of the experimental treatment (M3541 + RT) on FD 1 will be asked to continue to complete the BPI-SF as specified in the Schedules of Assessments (Table 1, Table 2, or Table 3 as appropriate). Subjects should complete the BPI-SF prior to any other study-related procedures. The subject should only rate pain and interference with daily activity as they relate to areas being irradiated as part of the experimental treatment. The Investigator must also ensure any new pain medication or change in ongoing pain medication (drug, dose, frequency, including any change in "as needed" dosing) is reported on the appropriate concomitant medications eCRF page.

The BPI-SF is a 9-item self-administered questionnaire used to evaluate the severity of the subject's pain and the impact of the pain on daily functioning. The subject is asked to rate their worst, least, average, and current pain intensity, and list current treatments and their perceived effectiveness. The subject is also asked to rate on a 1 to 10 scale the degree to which the pain interferes with general activity, mood, walking ability, normal work, relations with other persons, sleep, and enjoyment of life.

In general, pain related to tumor lesions irradiated in the context of this study, will be considered a concomitant medical condition and not considered an AE / SAE unless the pain is more severe than expected for the subject's condition (see Section 7.4.1.1 - AE / SAEs Observed in Association with Disease Progression).

Document No. CC Object No. CC

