# 5.1.1 Dose-limiting Toxicity

For this study, a DLT is defined as any of the following AEs that occur during the DLT evaluation period (except those that are clearly and incontrovertibly due to disease progression or extraneous causes), with severity graded according to the National Cancer Institute (NCI) Common Terminology Criteria for Adverse Events, Version 4.03 (CTCAE V4.03):

- Grade  $\geq$  3 non-hematologic toxicity, except:
  - $\circ$  Nausea, vomiting and / or diarrhea lasting  $\leq$  3 days in the once per FD and twice weekly schedules or 2 days in the thrice weekly schedule that can be medically managed
  - Worsening of pre-existing tumor pain associated with tumor lesions for which the subject is irradiated in the context of this study
- Evidence of treatment-related hepatocellular injury for > 3 days in the once per FD and twice weekly schedules and 2 days in the thrice weekly schedule, such as ≥ 5 × the upper limit of normal (ULN) of alanine aminotransferase (ALT) or aspartate aminotransferase (AST) and without any other apparent clinical causality
- Any occurrence of Hy's law (defined as aminotransferases > 3 × ULN, alkaline phosphatase < 2 × ULN, total bilirubin ≥ 2 × ULN, with no other reason to account for these abnormalities)
- Febrile neutropenia or Grade 4 neutropenia lasting for > 5 days, Grade 4 thrombocytopenia or any requirement for platelet transfusion (as defined by Grade 4 thrombocytopenia lasting for > 5 days or Grade ≥ 3 thrombocytopenia with bleeding), Grade 4 anemia that is unexplained by the underlying disease
- Any toxicity related to study treatment that causes the subject to interrupt treatment (defined as having to delay the next scheduled M3541 administration) for:
  - $\circ \geq 4$  FDs in the once per FD dosing schedule.
  - $\circ$  > 1 FD in the thrice weekly schedule
  - not to be able to be treated within 24 hours of the scheduled treatment time in the twice weekly schedule
- A related treatment-emergent adverse event (TEAE) that in the opinion of the SMC is of potential clinical significance such that further dose escalation would expose subjects to unacceptable risk.

Information on DLTs will be sent by the Sponsor or delegate to the SMC core members within 1 working day of the receipt of documented information.

Document No. CC Object No. CC

Dose escalation of M3541 will start from 50 mg orally once per FD until 1 of the following stopping rules apply:

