#### 7.4 Assessment of Safety

The safety profile of the IMP will be assessed through the recording, reporting and analysis of baseline medical conditions, AEs, physical examination findings including vital signs and laboratory tests as specified in the Schedule of Assessments (see Table 1). Special attention will be paid, during the exam as well as the interpretation of the laboratory results, to the organs which are positioned in the irradiation field. Worsening of a condition within an irradiated area (eg, skin reactions, bleeding) during the DLT evaluation period should be reported as a TEAE with grade and relatedness to RT and / or M3541. Improvements of disease-related symptoms should also be reported as improvement of the observed concomitant condition within an irradiated area (eg, improved pain, reduced bleeding) should be reported on the appropriate efficacy-related eCRF page.

Comprehensive assessment of any apparent toxicity experienced by each subject will be performed from the time of giving informed consent and throughout the study. The Investigator will report any AEs, whether observed by the Investigator or reported by the subject (see Section 7.4.1.2). The reporting period for AEs is described in Section 7.4.1.3.

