#### 8.5.1 General Considerations

All data recorded during the study will be presented in individual data listings performed on the Safety Analysis Set. All data will be evaluated as observed, and no imputation method for missing values will be used unless otherwise specified in the SAP. All data will be presented in a descriptive manner. Each cohort will be analyzed separately, and no multiplicity adjustment across cohorts will be performed.

Descriptive statistics will be used to summarize the study results, that is, statistics for continuous variables may include means, medians, ranges, and appropriate measures of variability. Qualitative variables will be summarized by counts and percentages. The uncertainty of estimates will be assessed by confidence intervals. Unless otherwise specified, the calculation of proportions will be based on the sample size of the analysis set of interest. Counts of missing observations will be included in the denominator and presented as a separate category if not otherwise specified in the SAP.

The DLT Analysis Set is the underlying data set for the MTD determination. Safety analyses will be performed on the Safety Analysis Set. Baseline summaries and efficacy analyses will be performed on the Safety Analysis Set. Analyses of PK variables will be performed on the PK Analysis Set. Analyses of biomarkers will be performed on the respective Biomarker Analysis Sets.

Posterior distribution and recommended next dose level will be calculated using EAST Version 6.4 or higher. The estimation of PK parameters will be performed using WinNonlin® Version 6.4 or higher. All other statistical analyses will be performed using SAS® Version 9.2 or higher, or R, Version 3.0.2 or higher.

Data cut-off for the primary analyses is defined by the completion of DLT evaluation period of the last subject in the last cohort.

The final analysis will be performed when the study has been completed (see Section 5.7).

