16.3 Patient-Reported Outcomes

Population: SAF Analysis Set

The Brief Pain Inventory - Short Form (BPI-SF) is a 9-item self-administered questionnaire used to evaluate the severity of the subject's pain and the impact of the pain on daily functioning. The subject is asked to rate their worst, least, average, and current pain intensity, and list current treatments and their perceived effectiveness. The subject is also asked to rate on a 1 to 10 scale the degree to which the pain interferes with general activity, mood, walking ability, normal work, relations with other persons, sleep, and enjoyment of life.

Analyses of BPI-SF questionnaire will be based on "Quality of life questionnaire - BPI-SF" eCRF page. Questionnaire data refer only to areas being irradiated as part of the experimental treatment.

Questionnaire results collected on FD 1 prior to any other study-related assessments will be used as baseline. Only subjects with cancer pain at baseline will be included in the analysis.

As suggested in the user guide⁽⁵⁾ provided by questionnaire developers, only the following 5 items will be summarized:

- 3 Please rate your pain by marking the box beside the number that best describes your pain at its **worst** in the last 24 hours.
- 4 Please rate your pain by marking the box beside the number that best describes your pain at its least in the last 24 hours.
- 5 Please rate your pain by marking the box beside the number that best describes your pain on the **average**.
- 6 Please rate your pain by marking the box beside the number that tells how much pain you have **right now**.
- 9 Mark the box beside the number that describes how, during the past 24 hours, pain has interfered with your: general activity, mood, walking ability, normal work, relations with other people, sleep, enjoyment of life.

Absolute values answered to questions 3 to 6 will be used for graphical representation. BPI pain interference (question 9) will be evaluated following two complementary approaches:

- Overall: it will be scored as the mean of the seven interference items. This mean will be used only if more than 50%, or four out of seven, of the total items have been completed on a given administration day, otherwise it will be set to missing.

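### New or worsened pain in an irradiated lesion is generally not an AE under Protocol 7.4.5 but is one under 7.4.1.1 and 7.4.4, so whether it is counted depends on the section a site follows

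*Protocol*

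**What the plan says.** Protocol 7.4.5 (Tumor Pain) states that, in general, pain related to the lesions irradiated under the protocol "will be considered a concomitant medical condition and not considered an AE / SAE unless the pain is more severe than expected", with the individual subject's condition as the yardstick. It refers the reader to the disease-progression rule in 7.4.1.1. Under that rule, progression and its signs and symptoms "should not be reported as an AE / SAE, unless the subject's general condition is more severe than expected for the subject's condition", or unless the outcome is fatal.

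Other places set different tests:

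- Protocol 7.4.1.1, on events that are not AEs, exempts "Medical conditions present at the initial study visit (such as pain) that do not worsen in severity or frequency during the study". Worsened baseline pain falls outside this exemption.
- Protocol 7.4.4 requires AE reporting, whatever the relationship to treatment, of "All newly diagnosed or worsening conditions, signs and symptoms observed after the signing of the ICF".
- Protocol 7.4 and Table 1 footnote j carry the same sentence: "Worsening of a condition within an irradiated area (eg, skin reactions, bleeding) during the DLT evaluation period should be reported as a TEAE", graded and attributed to RT, M3541 or both.
- Protocol 5.1.1 defines a DLT as a type of AE. From the Grade 3 or higher non-hematologic criterion it exempts "Worsening of pre-existing tumor pain associated with tumor lesions for which the subject is irradiated in the context of this study".

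SAP 15.1.1 takes DLTs from the AE eCRF page, and SAP 15.2.1 takes the TEAE and SAE frequency tables from the same source. For the pain questionnaire (BPI-SF), SAP 16.3 states: "Only subjects with cancer pain at baseline will be included in the analysis".

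**The concern.** M3541 is given to strengthen the local effect of radiotherapy (Protocol 3.1.3), so pain arising or worsening in an irradiated lesion is a plausible local toxicity that the safety tables should show by dose level. If one section keeps it off the AE page and another puts it on, the count reflects which section the site applied. Where 7.4.5 is applied it can only lower the count, so any bias is toward apparent tolerability. The TEAE, Grade 3 or higher and SAE endpoints are exposed. The primary endpoint is exposed more narrowly, because an event that is not an AE cannot be a DLT.

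**Working it through.** No stated figure is at issue. All data are summarized without hypothesis tests (Protocol 8.5.1: "All data will be presented in a descriptive manner"). The check is to run each type of irradiated-lesion pain through the rules.

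| Pain in an irradiated lesion | 7.4.5 | 7.4.1.1 and 7.4.4 | Grade 3 or higher DLT criterion, 5.1.1 | Result |
|---|---|---|---|---|
| Present at baseline, not worse | Not an AE | Not an AE | Does not arise | Agree |
| Pre-existing, worsened, judged expected | Not an AE | AE | Exempt | Conflict in TEAE/SAE tables |
| New, below Grade 3, judged expected | Not an AE | AE | Below threshold | Conflict in TEAE/SAE tables |
| New, Grade 3 or higher, judged expected | Not an AE | AE | Not exempt | Conflict in TEAE/SAE tables and DLT count |
| New or worsened, judged more severe than expected | AE | AE | As 5.1.1 | Agree |
| Attributed to progression | Not an AE unless pain is worse than expected | Not an AE under the progression rule unless the general condition is worse than expected or the outcome is fatal | Excluded only if clearly and incontrovertibly due to progression | Broadly agree |

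Three points follow.

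1. The middle rows turn on the word *expected*, which has no anchor. 7.4.5 takes the idea from the progression rule but drops the condition that there be progression.
2. The 5.1.1 exemption for worsening of pre-existing pain is needed only if such worsening is otherwise an AE. Where 7.4.5 applies, that exemption has nothing to do. The two sections were not written to the same rule.
3. Neither document resolves the conflict downstream, since the SAP outputs start from the AE page. A subject whose pain is not recorded as a DLT and who receives less than 80% of planned dosing would also leave the DLT Analysis Set (Protocol 8.4) and be replaced (5.5.2).

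**Other visibility.** Subjects with cancer pain on FD 1 complete the BPI-SF on each later FD and on PTD 15 and PTD 30 (Table 1 footnote f). SAP 16.3 plots these scores by dose level with changes in pain therapy marked. Pain-medication changes for irradiated lesions are recorded (Protocol 6.5), and the pain-therapy listing shows dose level (SAP 12.5). A subject without pain on FD 1 is not asked to repeat the BPI-SF. None of these outputs gives a graded, attributed event count.

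**Illustration for the narrow DLT path only.** The inputs are the Protocol 8.1 model, logit P(DLT) = α + exp(β) × log(d/d_ref), with prior means −0.847 and −0.279, SDs 1.007 and 1.636, and covariance 0 (normal priors assumed). The data are 0/3 DLTs at 50 mg and 0/4 at 100 mg (Protocol 3.1.5), plus a hypothetical cohort of 3 at 200 mg. The documents do not give d_ref, so it is varied. The posterior was computed on a grid.

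| d_ref (mg) | P(DLT rate > 35%) at 200 mg, 1/3 recorded | Same, 0/3 recorded | Highest pre-planned dose under the 25% limit, 1/3 then 0/3 |
|---|---|---|---|
| 100 | 0.323 | 0.092 | 100, 300 mg |
| 200 | 0.260 | 0.076 | 100, 200 mg |
| 300 | 0.080 | 0.012 | 200, 300 mg |
| 500 | 0.043 | 0.004 | 300, 300 mg |
| 800 | 0.031 | 0.002 | 500, 500 mg |

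One unrecorded DLT can change what the model admits for some values of d_ref and not for others.

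**The case against.** The best defense is that 7.4.5 concerns disease pain. It is titled Tumor Pain, it speaks of the subject's condition, and it points to the progression rule. Keeping such pain out of the AE tables is a sensible aim in a palliative radiotherapy trial. Treatment effects in the field have their own provisions, in Table 7 and in the in-field worsening sentence. The rule is also qualified by the words *in general* and by the exception for pain worse than expected. This is a possible reading, and the aim is reasonable, but 7.4.5 does not say that it is limited to disease pain or to progression. An investigator who applies it to a pain flare after radiotherapy is within its wording.

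Some stronger inferences should be resisted:

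- A reader might infer that new-onset Grade 3 or higher pain is never an AE under 7.4.5. Such pain, in a subject who was pain-free on FD 1, may well be judged more severe than expected and so be reported.
- A reader might infer that in-field pain disappears from the data by dose level. The BPI-SF plots and medication records show part of it, mainly for subjects with pain on FD 1, and the SMC reviews all available safety data.
- A reader might count 7.4 and footnote j as two further flat contradictions. They are one repeated sentence. Its examples of worsening are skin reactions and bleeding, and pain appears only among the examples of improvement. It sits poorly with 7.4.5 but does not settle the matter.

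**Conclusion.** The inconsistency is real and unresolved in the current text. 7.4.5 conflicts directly with 7.4.1.1 for worsened baseline pain and with 7.4.4 for new or worsened pain, and its exemption is broader than the one in 5.1.1. The consequence is that TEAE and SAE counts for irradiated-lesion pain can depend on the site. The DLT count is affected only when new-onset Grade 3 or higher pain is judged expected, which should be uncommon.

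The size cannot be quantified. The documents give neither an incidence of such pain nor the chance that an investigator would call it expected, and both would be needed. The model illustration rests on a hypothetical cohort and an assumed d_ref, and the SMC is not bound by the model. It shows that one event can matter, not that dose selection has been or will be distorted. This should be corrected, but it is a reporting-rule repair and not a flaw in the design.

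**What to change.** Reconcile 7.4.5 with the three parts of the protocol that it touches: the baseline-condition and progression rules in 7.4.1.1, and 7.4.4. Limit its exemption to irradiated-lesion pain that either was present at baseline and has not worsened, or is attributed to disease progression under the existing 7.4.1.1 rule. Record other new or worsened irradiated-lesion pain on the AE page, with CTCAE grade and relationship to M3541 and to RT, and apply the SAE criteria as usual. The progression limb is needed, because without it the revised sentence would contradict the progression rule.

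Leave the 5.1.1 DLT exemption unchanged. The SAP needs no change, because its tables already read the AE page. The cost is an edit to one sentence in 7.4.5 and some additional low-grade pain AEs to record.
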